Statistical Analysis Plan (Short)

Comparative effect of two educational videos for people with knee osteoarthritis (vidEO): An online randomised controlled trial

Version: 2

Author/s of SAP: [name] and [name] (Biostatisticians, Centre for Epidemiology and Biostatistics), University of Melbourne
[name], CHESM, University of Melbourne

Date of SAP: 14/12/2021

Author/s of template: [name] (Deputy Head MISCH Biostatistics), University of Melbourne (Template adapted from www.pfizer.com)

Date of template: 25/10/2021

[figure not shown]
Table of Contents

1 Introduction	3
2 Data Source	4
3 Analysis Objectives.....	5
3.1 Aim 1	5
3.2 Aim 2	5
3.3 Aim 3	5
4 Analysis sets/Populations/Subgroups.....	5
5 Endpoints and Covariates	6
6 Handling of Missing Values and Other Data Conventions	6
7 Statistical Methodology	7
7.1 Statistical Procedures.....	7
7.1.1 Aim 1	7
7.1.2 Aim 2	7
7.1.3 Aim 3	Error! Bookmark not defined.
7.2 Measures to Adjust for Multiplicity, Confounders, Heterogeneity	8
8 Sensitivity Analyses	8
9 QC Plans	8
10 Programming Plans	8
11 References	8
Appendix 1	9
Appendix 2	16
Appendix 3	18

1 Introduction

Objectives	To determine if an educational video based on an empowerment and participatory discourse improves self-efficacy to manage knee OA pain and reduced fear of movement more than an educational video based on a disease information and impairment discourse, among people with knee osteoarthritis symptoms.
Study Design	Two-arm, parallel groups superiority randomised controlled trial
Planned Sample Size	516
Study Procedures	Our trial will be delivered via an online survey (Qualtrics, Provo, UT, USA) and Vimeo (Vimeo Inc, NYC, USA) video sharing platform. Volunteers will be recruited by a digital survey-based research company (Cint PTY LTD) and complete an online screening survey. Eligible participants will then be invited to read the information sheet and digitally consent to participate in the study. They will provide demographic information and answer the baseline questionnaires. They will then be randomised to one of two intervention groups. On the next page of the survey they will be presented with a video to watch before moving on the post-intervention questionnaire.
Duration of the study	Anticipated participant recruitment start: November 2021 Anticipated data collection end: December 2021 Recruitment for this study is anticipated to take approximately 3-4 weeks.

Figure 1. Study chart

2 Data Source

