5.2 Secondary Outcomes

- Level of Concern (ordinal, range 0=Not at all concerned – 4=Extremely concerned, measured at baseline and post-intervention)
- Change in Credibility/expectation questionnaire – Part 1 (post-intervention minus baseline)
- Change in Credibility/expectation questionnaire – Part 2 (post-intervention minus baseline)
- Change in Importance of physical activity (post-intervention minus baseline)
- Change in Motivation to be physically active (post-intervention minus baseline)
- Change in Knee osteoarthritis knowledge scale (post-intervention minus baseline)
- Perceived likelihood of needing surgery (ordinal, measured at baseline and post-intervention)
- Perceived change in hope (binary, only measured at post-intervention)
- Satisfaction with meeting information needs (ordinal, only measured at post-intervention)

6 Handling of Missing Values and Other Data Conventions

An appendix table will provide summaries of baseline characteristics and baseline levels of primary and secondary outcomes where measured between two groups: those participants who provide both primary outcomes post-intervention, and those participants who are missing either or both primary outcomes. If less than 5% of both primary outcomes is missing, analyses will be performed on complete case data (Lawford et al, Under review; Sharma et al., 2021). If greater than 5% of either primary outcome is missing, multiple imputation will be applied for the primary analysis. Missing outcomes will be imputed using chained equations with predictive mean matching and five nearest neighbours for continuous outcomes. Imputation models for continuous outcomes post-intervention will include all primary and secondary outcomes at both baseline and post-intervention,

along with age, gender, BMI, education level, geographical location, employment status, duration of symptoms, ethnicity, personal relevance and pain during walking. Data will be imputed for each treatment group separately. The number of imputed data sets created will be based on the percentage of patients in the sample with missing outcome data (e.g., 15 imputed datasets if 15% of participants have missing data). Estimates from the imputed datasets will be combined using Rubin's rules. (Carpenter JG, Kenward MG. Multiple imputation and its application. West Sussex, UK: John Wiley & Sons Ltd; 2013.)

7 Statistical Methodology

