7.1 Statistical Procedures

A biostatistician ([name], supervised by [name]) will analyse de-identified data in Stata version 16.1 (StataCorp LLC, College Station, TX, USA), while blind to group allocation. Descriptive data will be presented by intervention group as mean (SD), median (IQR) or n (%) as appropriate. Comparative analyses between groups will be performed using intention-to-treat according to the group to which the participant was randomised, irrespective of whether they adhered to the intervention. The number included in each analysis will be reported. Standard diagnostic plots will be used to check model assumptions, including assessing linearity and homoscedasticity, where appropriate.

7.1.1 Aim 1

Separate linear regression models for each primary outcome will be used to estimate the between-group mean (95% CI) difference in change scores (either baseline minus post-intervention or post-intervention minus baseline, so that positive values favour the experimental group (allocated the 'empowerment and participatory discourse' video), adjusted for the outcome at baseline. Post-intervention time point was 'immediately following watching the video'.

7.1.2 Aim 2

Separate linear regression models for each continuous secondary outcome will be used to estimate the between-group mean (95% CI) difference in change scores (post-intervention minus baseline, so that positive values favour the experimental 'empowerment and participatory discourse' group), adjusted for the outcome at baseline. For the binary secondary outcome, perceived change, groups will be compared using logistic regression, with results reported as risk differences and risk ratios, with corresponding 95% CIs. For ordinal secondary outcomes, ordinal logistic regression models will be fitted similarly, adjusted for the outcome at baseline where able. The proportional odds

assumption will be assessed using the Brant test. If proportional odds cannot be assumed, multinomial regression models will be fitted. Results will be reported as odds ratios, or relative risk ratios if multinomial regression is used, with corresponding 95% CIs.

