^e Logistic regression model fitted, unadjusted.

^f Ordinal logistic regression models fitted, adjusted for the outcome at baseline where able, as proportional odds could be assumed. Odds ratios > 1 favour Group 2.

^g Multinomial regression models fitted, adjusted for the outcome at baseline where able, as proportional odds could not be assumed. Relative risk ratios > 1 favour Group 2.

^h Question asked “How concerned are you about your knee problem?”

SD = standard deviation.

ASES = Arthritis Self-efficacy Scale (Pain subscale); scored 0-10, with higher scores indicating greater self-efficacy.

BFMS= Brief Fear of Movement Scale for Osteoarthritis; scored 6-24, with higher scores indicating greater fear.

Appendix 1. Baseline characteristics and outcome summary measures of participants who did and did not complete both primary outcomes, reported as mean (standard deviation) unless otherwise stated.

Domain	Units / categories	Completed both primary outcomes [N = xxx]	Incomplete one or both primary outcomes [N = xxx]
Age	Years		
Gender, n (%)	Male		
	Female		
	Non-binary		
	Other (please specify)		
	Prefer not to say		
State/territory, n (%)	Australian Capital Territory		
	New South Wales		
	Northern Territory		
	Queensland		
	South Australia		
	Tasmania		
	Victoria		
	Western Australia		
Geographical location ^a , n (%)	Major city		
	Inner regional		
	Outer regional		
	Remote		
	Very remote		
Height	Metres		
Weight	Kilograms		
Body mass index	kg/m ²		
Level of education, n (%)	<3 years of secondary education (high school)		
	3 or more years of secondary education (high school)		
	Some education beyond high school e.g., trade/technical/vocational training		

	Completed tertiary education (college or university)
Current employment situation, n (%)	Unemployed/not employed/ e.g., full-time carer, full-time student
	Retired (not due to health reasons)
	Unable to work due to health reasons
	Paid work part time
	Paid work full time
Ethnicity, n (%)	Australian/New Zealand
	Aboriginal and Torres Strait Islander
	European
	Asian
	Other Oceania
	North African & Middle Eastern
	Sub-Saharan Africa
	North American
	South American
	Other
Pain severity during walking ^b	0-10
Pain duration, n (%)	Less than one year
	One to two years
	Two to five years
	Five to ten years
	Ten to fifteen years
	Fifteen to twenty years
	More than twenty years
Where received OA information ^c , n (%)	No information received
	GP or family doctor
	Orthopaedic surgeon

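### Hope is compared without covariates; adjusting for related baseline items would cost little and might modestly narrow its interval

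*SAP*

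**What the plan says.** Section 5.2 lists the outcome as "Perceived change in hope (binary, only measured at post-intervention". Section 7.1.2 gives its model: "For the binary secondary outcome, perceived change, groups will be compared using logistic regression, with results reported as risk differences and risk ratios". No covariate is named there. Footnote e to Table 2 in the table templates settles the matter: "Logistic regression model fitted, unadjusted".

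Of the eleven outcomes in sections 5.1 and 5.2, nine have a baseline measurement, and their models are adjusted for it. The two measured only after the video are hope and satisfaction.

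The Study Procedures row in section 1 places the demographic and baseline questionnaires before randomisation. Appendix 1 lists the items. Two lie close in content to hope after an educational video: CEQ Part 2, which includes the expected change in knee pain over one year, and personal relevance of education about knee osteoarthritis. Section 6 already uses baseline variables as predictors: its imputation models for continuous outcomes take in the baseline outcome scores, "along with age, gender, BMI, education level, geographical location, employment status, duration of symptoms, ethnicity, personal relevance and pain during walking".

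Section 7.2 calls the secondary outcomes exploratory, says the trial was not powered for them, and promises effect sizes, intervals and p values so that readers can weigh the results themselves.

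**The concern.** The SAP adjusts wherever the same item was asked at baseline. Lack of an identical baseline item is not in itself a statistical reason to leave out other pre-randomisation predictors. If people who start with a better outlook, or who find the topic more relevant, are more likely to report increased hope, some of the person-to-person variation in the answer can be explained. An adjusted, standardised risk difference would then vary less than the raw one.

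At stake is only the width of one interval. Because section 7.2 leaves the weighing of secondary results to the reader, that interval is much of what the analysis delivers. Fixing the covariates in advance also removes any temptation to choose them later if the arms happen to differ in outlook.

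**Working it through.** **Inputs from the SAP.** "Planned Sample Size 516" (section 1). The allocation ratio is not stated; 1:1, so 516 / 2 = 258 per arm, is assumed. The SAP gives no expected proportion of hopeful participants, no effect size and no association between a baseline item and hope. All of these are assumed below, and there is no figure in the plan to reproduce on this point.

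**Approximate formula.** The unadjusted standard error of the risk difference is √[p₁(1−p₁)/258 + p₂(1−p₂)/258]. With 50% against 60% hopeful:

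√[(0.25 + 0.24)/258] = 0.0436, so the 95% half-width is 1.96 × 0.0436 = 8.54 percentage points.

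If baseline covariates explain a share R² of the variation, the adjusted half-width is about 8.54 × √(1−R²), and the equivalent sample size is 516/(1−R²):

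| R² (assumed) | Half-width, points | Narrower by | Equivalent N |
|---|---|---|---|
| 0 | 8.54 | 0% | 516 |
| 0.02 | 8.46 | 1.0% | 527 |
| 0.05 | 8.33 | 2.5% | 543 |
| 0.10 | 8.10 | 5.1% | 573 |
| 0.20 | 7.64 | 10.6% | 645 |

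**Simulation.** 3,000 trials per setting, 258 per arm. The probability of a hopeful answer was expit(−0.2 + 0.5·t + b·x), with t the arm and x one standard normal baseline score; expit(−0.2) = 0.45 in the reference arm at an average score. The raw risk difference was compared with the one standardised from a logistic model on t and x. The interval narrows by 1 − 1/√(variance ratio), the ratio being unadjusted over adjusted.

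| b | AUC of x | Variance ratio | Narrower by | Repeat run: ratio | Narrower by |
|---|---|---|---|---|---|
| 0.3 | 0.58 | 1.03 | 1.5% | 1.02 | 1.0% |
| 0.5 | 0.63–0.64 | 1.07 | 3.3% | 1.06 | 2.9% |
| 0.75 | 0.69 | 1.14 | 6.3% | 1.12 | 5.5% |
| 1.0 | 0.74 | 1.22 | 9.5% | 1.19 | 8.3% |

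In the repeat run, the mean raw and standardised risk differences both matched the true marginal value, and interval coverage was 94–95%. Adjustment therefore leaves the meaning of the risk difference unchanged. With a useless covariate the ratio was 0.997. With the signal spread over five covariates it was 1.00 at AUC 0.58 and 1.05 at AUC 0.63, which argues for a short list. The risk ratio was not simulated separately; it is built from the same two averaged risks.

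**Scale matters.** In a further simulation (1,500 trials per setting, 516 participants), the standard error of the standardised risk difference fell from 0.0435 to 0.0431, 0.0437 to 0.0421 and 0.0425 to 0.0389 as R² rose through 0.02, 0.08 and 0.17. On the log odds ratio scale, adjustment raised it from 0.178 to 0.181, 0.186 and 0.196. The narrowing appears only if the adjusted model is converted to the marginal risk difference that the SAP reports.

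**The case against.** **The plan contains no error here.** In a randomised comparison the unadjusted model is valid, and footnote e discloses it. A reader might infer that a chance imbalance in outlook would bias the result. It would not: such imbalance is ordinary sampling variation that the 95% interval already covers. This stands in full.

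**The gain is unproven.** A reader might infer that precision is certainly being lost. The SAP contains nothing to show it. The item in Appendix 1 asks how hope has changed since the video, not how hopeful the person is, so baseline outlook may predict it poorly. The upper AUC values have no support in the document, and at R² of 0.05 or less the interval narrows by 2.5% at most. This limits the size of the claim but does not remove it, because a useless covariate costs almost nothing.

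**The outcome is exploratory.** Section 7.2 makes power no design target, so an argument from power carries little weight. Interval width still matters under the reporting approach chosen there.

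**The reason is not given.** For hope the SAP says only that the model is unadjusted. That this follows from the missing baseline item is an inference.

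**Satisfaction.** It is tempting to extend the point to "Satisfaction with meeting information needs (ordinal, only measured at post-intervention". The rule there is "For ordinal secondary outcomes, ordinal logistic regression models will be fitted similarly, adjusted for the outcome at baseline where able", and with no baseline version no covariate enters. But satisfaction is reported as an odds ratio. In 200 simulated trials per setting, adjustment moved the standard error of the log odds ratio from 0.159 to 0.160 for a weak or moderate covariate and from 0.158 to 0.162 for a strong one, so it did not shrink. Power rose (0.54 to 0.58 moderate, 0.445 to 0.54 strong), but only through a larger, conditional odds ratio, which is a different quantity. Under the multinomial fallback, five outcome categories give four equations. An intercept and a treatment term make 4 × 2 = 8 parameters; adding five covariates makes 4 × 7 = 28, a burden if the end categories are sparse. The precision argument does not carry over to satisfaction.

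**Conclusion.** The point holds for hope alone, as an optional efficiency gain of low severity. The planned comparison is valid. Its risk difference and risk ratio may be somewhat less precise than the collected baseline data allow: about 1% to 10% in interval width for the risk difference if the baseline score has an AUC of 0.58 to 0.74, and nothing if the baseline items do not predict the answer. These figures rest on 1:1 allocation, an assumed hopeful proportion and effect, and an assumed prognostic strength, none of which the SAP gives. The primary analyses are not affected.

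**What to change.** In section 7.1.2 and footnote e, name a short list of baseline covariates closest in content to hope, for example CEQ Part 2 and personal relevance, and say how each is entered. State that the risk difference and risk ratio come from averaging predicted risks over the whole sample under each arm, with delta-method confidence intervals. Keep the unadjusted result as a supporting line. Leave the satisfaction model and footnotes f and g as they are.

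The cost is a few lines of wording. No new data are needed, and obtaining risk differences and risk ratios from a logistic model already requires a post-estimation step. A participant with a missing covariate would drop out of the adjusted model unless the SAP says otherwise, so that handling should be stated. Section 7.1 already commits to reporting the number in each analysis.

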Satisfaction that video met information needs *	
How satisfied are you that the video helped meet your current needs for information about your knee pain?
 
very unsatisfied moderately unsatisfied neutral moderately satisfied very satisfied
	
Likert scale with 5 response options. N (%) in each category

Perceived personal chance of ever needing knee replacement surgery	
How likely do you think you are of needing knee replacement surgery in the future?
 
1 = very unlikely to need surgery 2 = unlikely to need surgery 3 = neutral 4 = likely to need surgery 5 = very likely to need surgery
	
Likert scale with 5 response options. N (%) in each category

NRS = Numerical rating scale

* Only measured post-intervention (not baseline)

Appendix 2

DEFINITIONS OF DERIVED VARIABLES IN THE DATA SET

Variable in data set	Unit	Variable label in spreadsheet	Calculation	Range	Better
Arthritis Self Efficacy Scale – Pain Subscale	5 items, 0-10	ASES	Average	0-10	↑
Brief Fear of Movement Scale for Osteoarthritis	6 items, 1-4	BFMS	Summed	6-24	↓
Level of concern	Single item, 0-4 (ordinal)	Concern	n/a	0-4	↓
Credibility/expectation questionnaire – Part 1	3 items, 1-9	CEQp1	Summed	3-27	↑
Credibility/expectation questionnaire – Part 2	2 items, 1) 1-9 2) -4 to +4	CEQp2	Summed, item 2 transformed to 1-9	2-18	↑
Importance of physical activity	4 items, 1-5	ImpPA	Averaged, items 1 & 2 reverse scored	1-5	↑
Motivation to be physically active	Single item, 0-10	MotPA	n/a	0-10	↑
Knee osteoarthritis knowledge scale	11 items	KOAKS	Summed, items 1,2, 3, 4, 7, & 11 reverse scored.	11-55	↑
Likelihood of needing surgery	Single item, 1-5 (ordinal)	Surgery	n/a	1-5	↓
Perceived change in hope (binary, only measured post-intervention)	Single item, 5 levels	Hope	Dichotomised, 1-3 = not more	0 or 1	1

			hopeful (0), 4-5 = more hopeful (1)		
Satisfaction with meeting information needs	Single item, 5 levels (ordinal)	Satisfaction	n/a	1-5	↑

Table 1. Baseline characteristics of participants by group, reported as mean (standard deviation) unless otherwise stated.

Domain	Units / categories	Group 1 [N = xxx]	Group 2 [N = xxx]
Age	Years		
Gender, n (%)	Male Female Other / Prefer not to say Non-binary		
State/territory, n (%)	Australian Capital Territory New South Wales Northern Territory Queensland South Australia Tasmania Victoria Western Australia		
Geographical location ^a , n (%)	Major city Inner regional Outer regional Remote Very remote		
Height	Metres		

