Part 1, range 3-27								
Part 2, range 2-18								
Importance of physical activity, range 1-5								
Motivation to be physically active, range 0-10								
Knee Osteoarthritis Knowledge Scale, range 11-55								
	Baseline, counts (proportions)		Post-intervention, counts (proportions)		Between-group (n=xxx)			

	Group 1 (n=xxx)	Group 2 (n=xxx)	Group 1 (n=xxx)	Group 2 (n=xxx)	Relative risk ^c [95% CI]	P-value	Risk difference ^d [95% CI]	P- value
Perceived change to more hopeful ^e	n/a	n/a						
	Baseline, counts (proportions)		Post-intervention, counts (proportions)		Between-group (n=xxx)			
	Group 1 (n=xxx)	Group 2 (n=xxx)	Group 1 (n=xxx)	Group 2 (n=xxx)	Odds ratio ^f [95% CI]	P-value	Relative risk ratio ^g [95% CI]	P- value
Level of concern ^h					OR [95% CI]	P	–	–
0=Not at all concerned					–	–	REFERENCE	–
1=A little concerned					–	–	RRR [95% CI]	P
2=Quite concerned					–	–	RRR [95% CI]	P
3=Very concerned					–	–	RRR [95% CI]	P
4=Extremely concerned					–	–	RRR [95% CI]	P
Perceived personal likelihood of ever needing knee replacement surgery					OR [95% CI]	P	–	–

1 = very unlikely to need surgery				–	–	REFERENCE	–
2 = unlikely to need surgery				–	–	RRR [95% CI]	P
3 = neutral				–	–	RRR [95% CI]	P
4 = likely to need surgery				–	–	RRR [95% CI]	P
5 = very likely to need surgery				–	–	RRR [95% CI]	P
Satisfaction that video met information needs				OR [95% CI]	P	–	–
1 = very unsatisfied	n/a	n/a		–	–	REFERENCE	–
2 = moderately unsatisfied	n/a	n/a		–	–	RRR [95% CI]	P
3 = neutral	n/a	n/a		–	–	RRR [95% CI]	P
4 = moderately satisfied	n/a	n/a		–	–	RRR [95% CI]	P
5 = very satisfied	n/a	n/a		–	–	RRR [95% CI]	P

^a Within-group change was calculated as post-intervention minus baseline for all continuous outcomes, except Brief Fear of Movement Scale for Osteoarthritis where the within-group change was calculated as baseline minus post-intervention, so that positive values indicate improvement.

^b Positive values favour Group 2. Mean (95% CI) difference in change between groups, adjusted for the outcome at baseline, estimated using separate regression models for each outcome.

^c Relative risks > 1 favour Group 2.

^d Risk differences > 0 favour Group 2.

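### Table 2 states that odds ratios and relative risk ratios above 1 favour Group 2 for every ordinal outcome, but for level of concern and likelihood of surgery the direction is the reverse

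*SAP*

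**What the plan says.** Section 7.1.2 of the SAP plans ordinal logistic regression for the ordinal secondary outcomes, replaced by multinomial regression where proportional odds cannot be assumed. Results are reported as odds ratios or relative risk ratios respectively.

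The only rule for reading these ratios is in the footnotes to Table 2. Footnote f, attached to the odds ratio column heading, says "Odds ratios > 1 favour Group 2". Footnote g, attached to the relative risk ratio column heading, says "Relative risk ratios > 1 favour Group 2". Because both hang on column headings, they cover level of concern, likelihood of needing surgery and satisfaction alike.

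Section 5.2 defines the first of these as "Level of Concern (ordinal, range 0=Not at all concerned – 4=Extremely concerned". Appendix 1 codes the surgery item from 1 (very unlikely) up to "5 = very likely to need surgery". Appendix 2 marks both as better when lower, with no calculation listed, and satisfaction as better when higher. In the Table 2 shell the row marked as reference is the lowest category for all three; for concern that is "0=Not at all concerned".

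**The concern.** One direction rule is applied to outcomes that run in opposite directions. The SAP handles this problem for the continuous outcomes: fear of movement is subtracted the other way round so that positive means improvement. It has no equivalent step for the two ordinal outcomes on which a low score is good.

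Reduced concern is the first of the secondary hypotheses in section 3.2. If the table is filled in as laid out and its footnotes are followed, a benefit of the experimental video on concern or on expected surgery would be labelled as favouring the comparator, and a harm as favouring the experimental video. Section 7.2 leaves the secondary results unadjusted and asks readers to weigh effect sizes and intervals themselves, so the direction label has to be right. The analyst is blind to allocation and cannot use the expected direction as a check.

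**Working it through.** The plan gives no figure to reproduce here; the question is one of sign.

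**Which contrast.** Footnotes b, c and d state that positive mean differences, relative risks above 1 and risk differences above 0 favour Group 2. The binary hope outcome is coded 1 = more hopeful, so the contrast in Table 2 is Group 2 versus Group 1.

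**Scales and reference rows.**

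| Outcome | Codes | Better (Appendix 2) | Reference row (Table 2) | Ratio above 1, Group 2 vs Group 1, means | Footnotes f and g correct? |
|---|---|---|---|---|---|
| Level of concern | 0–4 | lower | 0, the best | Group 2 worse | No |
| Likelihood of surgery | 1–5 | lower | 1, the best | Group 2 worse | No |
| Satisfaction | 1–5 | higher | 1, the worst | Group 2 better | Yes |

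**Odds ratio.** In the usual proportional-odds parameterisation, OR = odds(Y > k in Group 2) / odds(Y > k in Group 1). OR > 1 means Group 2 lies in higher categories, which for the first two outcomes are the worse ones.

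**Relative risk ratio.** RRR for category j = (p2j / p2,ref) / (p1j / p1,ref). With the best category as reference, RRR > 1 means relatively more of Group 2 in the worse category j.

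**Numerical illustration.** Assume (the documents give no distribution) that Group 1 falls 10/25/30/20/15% across concern 0 to 4, and give Group 2 a true benefit with a cumulative OR of 0.67.

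- Group 1 cumulative proportions are 0.10, 0.35, 0.65 and 0.85. Their odds are 0.111, 0.538, 1.857 and 5.667.
- Dividing these by 0.67 gives Group 2 odds of 0.166, 0.804, 2.772 and 8.458, hence a Group 2 distribution of 14.2/30.3/28.9/15.9/10.6%.
- RRR for category 1 = (0.303/0.142) / (0.25/0.10) = 0.85. Categories 2 to 4 give 0.68, 0.56 and 0.50 in the same way.

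The same steps for a range of true benefits, confirmed by fitting ordinal and multinomial models to data with these distributions:

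| True Group 2 benefit on concern (OR) | Fitted OR, as coded | RRRs, categories 1–4 vs 0 | Footnotes say | OR if reverse-coded |
|---|---|---|---|---|
| 0.80 | 0.80 | 0.92, 0.81, 0.73, 0.68 | favours Group 1 | 1.25 |
| 0.67 | 0.67 | 0.85, 0.68, 0.56, 0.50 | favours Group 1 | 1.49 |
| 0.50 | 0.50 | 0.74, 0.49, 0.36, 0.30 | favours Group 1 | 2.00 |

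For satisfaction, a Group 2 benefit with OR 1.5 on the same assumed Group 1 distribution gives RRRs of 1.13, 1.40, 1.72 and 2.02, so the footnotes are correct there. The sizes depend on the assumed distribution; the direction does not.

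**Could one rule fit all three?** Reversing the contrast to Group 1 versus Group 2 would put concern and surgery right, but it would make satisfaction wrong and break with footnotes c and d. No single rule works for the three outcomes as coded.

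**The case against.** The best counter-argument concerns the odds ratios. The calculation column in Appendix 2 describes how a score is formed, not how it is analysed: fear of movement is listed there only as a sum, with lower better, yet its change score is reversed in the analysis. Section 7.1.2 does not say in which direction the ordinal model is fitted, so footnote f might be read as a target the analyst is meant to meet by inverting the ratio where necessary. That reading is weak. The fear of movement reversal is written out in section 5.1, Appendix 1 and footnote a, and that convention is confined to continuous outcomes. Nothing comparable is written for the ordinal ones. It also cannot rescue footnote g, because the reference rows printed in the shell are the best categories.

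Three limiting points do stand. First, for any one outcome the odds ratio and the relative risk ratios are alternatives, so each affected outcome yields either one misread odds ratio or four misread relative risk ratios, not both. Second, only the label is wrong: the fitted model, estimate, interval and p-value are sound, and Table 2 also prints counts by labelled category, so a careful reader might notice. Third, both outcomes are secondary and described as exploratory.

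**Conclusion.** The concern holds. Footnotes f and g state the wrong direction for two of the three ordinal outcomes, level of concern and likelihood of surgery, and the right direction for satisfaction. For the relative risk ratios this follows from the reference rows in the table shell, given the Group 2 versus Group 1 contrast used in the rest of the table. For the odds ratios it also rests on the standard parameterisation, in which a value above 1 means higher categories, and on the absence of any stated reversal.

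The effect is a full reversal of interpretation for those two outcomes, whatever the size of the effect. The primary outcomes, alpha, sample size and handling of missing data are untouched. Since one affected outcome is a named secondary hypothesis and the correction is trivial, it should be made before the results are tabulated.

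**What to change.** The simplest change is to make footnotes f and g outcome-specific: for level of concern and likelihood of surgery, ratios below 1 favour Group 2; for satisfaction, ratios above 1 favour Group 2. It would help to add a sentence to section 7.1.2 stating that odds ratios are for being in a higher category, Group 2 versus Group 1. This costs two footnotes and one sentence, with no change to data, design or models.

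The alternative is to reverse-code for analysis (4 minus the score for concern, 6 minus the score for surgery) and make the worst category the multinomial reference, so that above 1 favours Group 2 throughout. This takes more editing: the reversal must be stated in Appendix 2, the better-direction arrows must match, the reference rows in Table 2 must move, and the codes in section 5.2 and Appendix 1 must be kept consistent. Reversing the codes without moving the reference rows would leave footnote g wrong.
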